9.4 Sample Size Justification

The dose escalation portion of this study is a design with no dose de-escalation. The sequential cohort enrollment characteristics of this design do not allow a fixed computation of sample size. In a previous study with subjects receiving a 200 µg dose radiolabeled at 5 mCi (i.e., the maximum dose planned for this study), zero (0) subjects had an ADR. Therefore, it is expected that no subjects will have an ADR in this study and that each cohort will enroll the planned sample size of subjects. With 2 cohorts of 4 subjects and one cohort of up to 6 subject, it is anticipated that the study will enroll up to n=14 subjects.

9.5 Statistical Analyses

9.5.1 Analysis Populations

The following analysis populations will be defined for the study:

- **Intent-to-Diagnose (ITD) Population** - Subjects who are enrolled in the study, injected with Tc 99m tilmanocept, and are imaged will be included in the ITD analysis population.
- **Safety Population** – All subjects who are enrolled in the study and are injected with Tc 99m tilmanocept will be included in the safety population.

All safety data analyses will be conducted on the safety population. All efficacy data analyses will be conducted on the ITD population.

9.5.2 Analysis of Baseline and Demographic Characteristics

The distribution of each baseline and demographic variable of interest will be summarized by dose cohort. Continuous variables will be summarized via mean, median, standard deviation, and range. Categorical variables will be summarized via counts and percentages. This analysis will be performed on the safety population.

9.5.3 Analysis of Efficacy Variables

The number and percentage of subjects with at least one biopsy-confirmed or clinically suspected KS lesion that has localized with Tc 99m tilmanocept by planar and/or SPECT/CT imaging will be

computed. A 95% exact confidence interval on the per subject localization rate will be computed. This analysis will be performed by dose.

Per region lesion localization of Tc 99m tilmanocept by planar and/or SPECT/CT imaging will be computed across all biopsy-confirmed or clinically suspected KS lesions of all subjects. A 95% exact confidence interval on per region lesion localization will be calculated. This analysis will be performed by dose.

Localization intensities of biopsied lesions will be summarized by descriptive statistics (mean, median, standard deviation, minimum, maximum and range) for each dose.

Per biopsied lesion proportion of CD206-expressing cells and quantity of CD206 as determined by histology and IHC fluorescence will be summarized by descriptive statistics (mean, median, standard deviation, minimum, maximum and range) for each dose.

Concordance between between IV and SC tilmanocept in biopsy-confirmed or clinically suspected KS lesion sites will be assessed with a cross-tabulation including the joint probability distribution. The site will be the sampling unit for this analysis. An exact version of McNemar's test will be performed, testing the null hypothesis

$$H_0: \pi_{IV} = \pi_{SC}$$

$$H_A: \pi_{IV} \neq \pi_{SC}$$

where π_{IV} and π_{SC} represent the probabilities of localization with IV (only) tilmanocept and localization with SC tilmanocept only respectively.

In addition, descriptive statistics will be generated relative to the concordance and reverse concordance of observed sites of discrete localization of Tc 99m tilmanocept following IV and SC administration.

The number and percentage of subjects with at least one anatomical site other than KS that has been localized with Tc 99m tilmanocept by SPECT imaging will be computed. A 95% exact confidence interval on the per subject localization rate will be computed. This analysis will be performed by dose and overall.

Locations showing localization of Tc 99m tilmanocept by planar and/or SPECT/CT imaging that are not locations of biopsy-confirmed or clinically suspected KS sites will be computed across all sites in all subjects. A 95% exact confidence interval on per location localization will be calculated. This analysis will be performed by dose and overall.

Other efficacy analyses will be described in the Statistical Analysis Plan (SAP) for the study.

9.5.4 Analysis of Safety Variables

The number and percentage of subjects with ADRs will be tabulated by dose group and overall.

All AEs will be observed for each subject from the time of signing of informed consent until exit from the study. A treatment emergent adverse event (TEAE) is defined as an adverse event whose start date is on or after the Tc 99m tilmanocept injection date and time. If the injection date and time and/or the AE start date are missing, the AE will be considered treatment emergent.

Prior to analysis, all AEs will be coded using the MedDRA coding dictionary. Based on these coded terms, treatment emergent AEs will be summarized by dose group and overall as follows:

- by system organ class and preferred terms
- by system organ class and preferred terms and relation to study drug
- by system organ class and preferred terms and severity

Observed and change from baseline vital sign parameters, ECG parameters and hematology, clinical chemistry and urinalysis parameters will be summarized using descriptive statistics (mean, median, standard deviation, minimum, maximum and range) by dose group and overall.

Other safety analyses will be described in the SAP for the study.

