8.6 Safety

8.6.1 Adverse Events

8.6.1.1 Definition of Adverse Event

The definitions below follow International Conference on Harmonization (ICH) – Good Clinical Practice (GCP) (see also ICH Guideline for Clinical Safety Data Management: Definitions and Standards for Expedited Reporting).

Adverse Event (AE)

An AE is defined as any untoward medical occurrence in a subject administered a pharmaceutical product and which does not necessarily have a causal relationship with this treatment. An AE can therefore be any unfavorable and unintended sign (including an abnormal laboratory finding), symptom, or disease temporally associated with the use of a medicinal (investigational) product, whether or not considered related to the medicinal (investigational) product.

Any clinically significant change in a condition (worsening) from screening that results in a change in subject management will be considered an AE and will be recorded on the AE page of the CRF.

By definition for this study, all untoward medical occurrences beginning on the day of Visit 2 Baseline (Day 1) through the Follow-up Phone Call are to be reported as AEs. AEs continuing after study completion will be followed to normalization or stabilization. Additionally, untoward medical events occurring prior to the day of Tc 99m tilmanocept administration will be collected and added to the subject's medical history unless they are related to a study procedure, in which case the event will be recorded as an AE. SAEs will be reported from the time of consent through the end of participation.

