8.6.1.3 Assessments and Documentation of Adverse Events

Attention shall be paid to the occurrence of AEs for the duration of subject participation. Events occurring prior to Visit 2 (day of Tc 99m tilmanocept administration) will be recorded in the subject's medical history unless determined to be related to the study procedure. Untoward medical events beginning on Visit 2 (day of Tc 99m tilmanocept administration) through the completion of the Follow-up Phone Call will be reported as adverse events. Thus, subjects should be closely observed by the investigator both during and after the evaluation.

Any AE (observed, volunteered, or elicited) should be recorded in detail in the source documentation.

The following information is required:

- The **date and time of onset** of any AE.
- The duration (the entire duration of an event or symptom, calculated from date of onset to date of end, if not recorded directly).
- The seriousness of the AE will be assessed by the investigator. If the investigator deems that an AE qualifies as an SAE, a special form provided by the sponsor should be completed and the event must be immediately reported to the sponsor. A definition of SAEs is provided in [Section 8.6.1.5](#).
- The maximum intensity (mild, moderate, or severe).
- Whether drug treatment was administered for the event, any specific drug treatment must be documented.
- The relationship of the AE to the investigational product and to study conduct (for definitions, see above).

The **outcome** of the AE (resolved, resolved with sequelae, not resolved, unknown, death).

AEs will be coded according to an internationally recognized dictionary (Medical Dictionary for Regulatory Activities [MedDRA]).

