8.6.2.3 Vital Signs

Vital signs comprise the measurement of body temperature, heart rate, respiration, and systolic and diastolic blood pressure. All measurements will be taken after the subject has been in a resting position for at least 1 minute.

Vital signs will be measured at screening and within 30 minutes before investigational product injection, and within 30 minutes post-injection.

Any clinically significant change from screening (worsening) that results in a change in subject management will be considered an AE and will be recorded on the AE page of the CRF.

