5.0 Analysis of Safety

Adverse Drug Reactions (ADRs) are defined as all noxious and unintended responses to a medicinal product related to any dose or dose regimen. The phrase 'responses to a medicinal product' means that a causal relationship between a medicinal product and an adverse event. The primary safety variable is the proportion of patients experiencing at least one ADR. The number and percentage of subjects with ADRs will be tabulated by dose group and overall. Other safety endpoints are noted below.

Analysis of Safety Endpoints

Attention shall be paid to the occurrence of adverse events (AEs) from the time of signing informed consent until exit from the study. Events occurring prior to Tc 99m tilmanocept administration will be recorded in the subject's medical history unless determined to be related to the study procedure. A treatment emergent adverse event (TEAE) is defined as an adverse event whose start date is on or after the first study drug administration date. If the study drug administration date and/or the AE start date are missing, the AE will be considered treatment emergent.

Prior to analysis, all AEs will be coded using the Medical Dictionary for Regulatory Activities (MedDRA). The MedDRA version used will be stated in the final validated tables. Based on these coded terms, AEs and TEAEs will be summarized by dose group and overall as follows:

- by system organ class and preferred terms;
- by system organ class and preferred terms and relation to study drug; and,
- by system organ class and preferred terms and severity.

In addition to the above endpoints, the following describes the analyses of the other safety data being collected for the study.

Vital Signs

Vital signs will include heart rate, blood pressure, respiration rate, and body temperature. Vital signs will be taken during screening, prior to study drug administration on Day 1 (and Day 7 [\pm 3] for Cohort 3), and within 30 minutes following study drug administration. For each vital sign, summary statistics

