Cohort	Subject No.	WHO Drug Preferred Term ^a / Verbatim Drug Name / Indication / ATC Level 1 Code / ATC Level 4 Code	Start Date	Stop Date	Route	Ongoing?
xxxxxx	xxxxxxx	xxxxxxxxxxxxxxxxxxxxxxxxxxxxxx xxxxxxxxxxxxxxxxxxxxxxxxxxxxxx xxxxxxxxxxxxxxxxxxxxxxxxxxxxxx xxxxxxxxxxxxxxxxxxxxxxxxxxxxxx xxxxxxxxxxxxxxxxxxxxxxxxxxxxxx	xxxxxx	xxxxxx	xxxxx	xxxxx
xxxxxx	xxxxxxx	xxxxxxxxxxxxxxxxxxxxxxxxxxxxxx xxxxxxxxxxxxxxxxxxxxxxxxxxxxxx xxxxxxxxxxxxxxxxxxxxxxxxxxxxxx xxxxxxxxxxxxxxxxxxxxxxxxxxxxxx xxxxxxxxxxxxxxxxxxxxxxxxxxxxxx	xxxxxx	xxxxxx	xxxxx	xxxxx

^a Concomitant medications coded with WHO Coding Dictionary xxxxxxxxx
Cohort 1 = 100µg/5mCi IV; Cohort 2 = 100µg/10mCi IV; Cohort 3 = 200µg/5mCi IV and SC.
STATKING Clinical Services (DD-MMM-YYYY)
Source Program: xxxxxxx.sas

Data Listing 8. Adverse Events Data Listing
 Navidea Biopharmaceuticals - Study No. NAV3-24
 Safety Population (N=xxxx)

Cohort	Subject No.	AE Start Date and Time/	Start Date and Time of most recent tilmanocept injection	MedDRA System Organ Class ^a / MedDRA Preferred Term/ CRF Verbatim Term	Treatment Emergent?	Adverse Drug Reaction (Y/N)	Severity	Relation to: Tc-99m tilmanocept/ Procedure	Serious	Outcome
		End Date and Time								
xxxxxx	xxxxxxxxxx	xxxxxxx	xxxxxxx	xxxxxxxxxxxxxxxxxxxx	xxx	xxx	xxxxxxxxxx	xxxxxxxxx/xxxxxxxxx	xxx	xxxxxxxxxx
		xxxxxxxx/	xxxxxxxx	xxxxxxxxxxxxxxxxxxxx						x
		xxxxxxxx		xxxxxxxxxxxxxxxxxxxx						
		xxxxxxxx		xxxxxxxxxxxxxxxxxxxx						
xxxxxx	xxxxxxxxxx	xxxxxxx	xxxxxxx	xxxxxxxxxxxxxxxxxxxx	xxx	xxx	xxxxxxxxxx	xxxxxxxxx/xxxxxxxxx	xxx	xxxxxxxxxx
		xxxxxxxx/	xxxxxxxx	xxxxxxxxxxxxxxxxxxxx						x
		xxxxxxxx		xxxxxxxxxxxxxxxxxxxx						
		xxxxxxxx		xxxxxxxxxxxxxxxxxxxx						

^a Adverse events coded with MedDRA Coding Dictionary Version xxx.

Cohort 1 = 100 μ g/5mCi IV; Cohort 2 = 100 μ g/10mCi IV; Cohort 3 = 200 μ g/5mCi IV and SC.

STATKING Clinical Services (DD-MMM-YYYY)

Source Program: xxxxxxx.sas

Page x of y

Data Listing 9. Subject Laboratory Profiles - Hematology Data Listing
Navidea Biopharmaceuticals - Study No. NAV3-24
Safety Population (N=xxx)

Cohort	Subject No.	Visit	Sample Date/ Time	Parameter (Units)	Result	Normal Range		Clin. Sig?
						Lab Low	Lab High	
xxxxxx	xxxx	xxxxxxxx	xxxxxxxx xx:xx	xxxxxxxxxxxx (xxx)	xxx	xxx	xxx	xxx
				xxxxxxxxxxxx (xxx)	xxx	xxx	xxx	xxx
				xxxxxxxxxxxx (xxx)	xxx	xxx	xxx	xxx
				xxxxxxxxxxxx (xxx)	xxx	xxx	xxx	xxx
				xxxxxxxxxxxx (xxx)	xxx	xxx	xxx	xxx
				xxxxxxxxxxxx (xxx)	xxx	xxx	xxx	xxx

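### Treatment-emergent status rests on onset alone and each AE keeps one maximum grade, so worsening after an injection can be missed and, in Cohort 3, cannot be attributed to the IV injection

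*Protocol*

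**What the plan says.** Three provisions work together.

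- **Definition of a TEAE.** Protocol 9.5.4 uses an event "defined as an adverse event whose start date is on or after the Tc 99m tilmanocept injection date and time". SAP 5.0 uses "an adverse event whose start date is on or after the first study drug administration date". Neither mentions worsening. The protocol compares date and time but does not say which injection applies in Cohort 3. The SAP compares the date only and names the first administration.
- **What is recorded per AE.** Protocol 8.6.1.3 asks for one date and time of onset and one intensity, worded as "The maximum intensity (mild, moderate, or severe". Nothing there tells the site to date a change of grade, or to open a new record, when an AE already open gets worse.
- **Worsening as an AE.** Protocol 8.6.1.1 has a partial rule: "Any clinically significant change in a condition (worsening) from screening that results in a change in subject management will be considered an AE". Section 8.6.2.3 repeats it for vital signs ("Any clinically significant change from screening (worsening) that results in a change in subject management will be considered an AE"), and 8.6.2.2 and 8.6.2.4 have similar rules for ECG and laboratory findings. Events before the injection day go to "medical history unless determined to be related to the study procedure".

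In the outputs, SAP Tables 16-21 (AEs, TEAEs, ADRs, SAEs) have a single Cohort 3 column. Tables 22-27 (vital signs, laboratory, ECG) show Cohort 3 IV and SC separately. The only AE output that links an event to one injection is Data Listing 8, through the column "Start Date and Time of most recent tilmanocept injection".

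**The concern.** A safety analysis should pick up an event that an injection brings on and also one that it makes worse. With one onset and one maximum grade per AE, an increase in severity has no date of its own, and the definitions would not use such a date if it existed.

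This matters most in Cohort 3. The primary objective in Protocol 2.1 concerns escalating IV doses, and Cohort 3 is the only cohort given 200 µg IV. Every Cohort 3 subject has already had 200 µg SC some days before. If a symptom is mild after SC and more severe after IV, the plan keeps one record with an onset after SC and a grade reached after IV. A reader asking what happened after the 200 µg IV injection could not recover the answer from the AE data.

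**Working it through.** No stated figure rests on this definition, so there is none to reproduce. The check applies each rule as written to the onset patterns that can arise.

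**Inputs**
- Protocol rule (9.5.4): onset date and time at or after injection date and time. I assume the first injection is meant, since the protocol does not say.
- SAP rule (5.0): onset date on or after the first administration date.
- Cohort 3 timing (Protocol 7.4 and 7.5): SC on Day 1, IV on Day 7 ± 3, that is Day 4 to Day 10. The interval is 4 − 1 = 3 to 10 − 1 = 9 days.
- Planned cohort sizes (Protocol 5.2 and 9.4): 4, 4 and up to 6, total 4 + 4 + 6 = 14.
- The onset patterns are illustrative and do not come from the documents.

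| Pattern | Protocol rule | SAP rule | Most recent injection at onset |
|---|---|---|---|
| 1. Procedure-related AE starting before Day 1, one record, worse after injection | not a TEAE | not a TEAE | none |
| 2. Onset on Day 1 before the injection, one record | not a TEAE | TEAE | none |
| 3. Screening condition whose worsening after the Day 1 injection changes management, entered as a new AE dated at the worsening | TEAE | TEAE | Day 1 injection |
| 4. Cohort 3: onset after SC, worse after IV, one record | TEAE | TEAE | SC |
| 5. Cohort 3: onset on the IV day before the IV injection | TEAE | TEAE | SC |
| 6. Cohort 3: worsening after IV entered as a new AE | TEAE | TEAE | IV |

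**What follows**
- Pattern 1 is missed by both documents. The two disagree on pattern 2, and there the SAP counts the event whether or not it worsens.
- Pattern 3 shows that 8.6.1.1 closes part of the gap. It needs a change in management, though, and 8.6.1.2 grades severity by tolerability and interference with usual activities. An AE can move from mild to moderate with no change in management. The rule also compares with screening and not with the state just before the IV injection. An event that began after SC is already worse than screening, so the rule does not clearly call for a second record.
- Patterns 4 and 6 are the same clinical course recorded in two ways. Only pattern 6 lets the worsening be linked to IV, and the protocol does not ask for it.

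**Size**
- Patterns 1 and 2: one missed subject with no other TEAE lowers the subject-level TEAE percentage by 1/4 = 25.0 points in Cohort 1 or 2, by 1/6 = 16.7 points in Cohort 3 at full size, and by 1/14 = 7.1 points overall. Pattern 2 is missed only under the protocol wording. The documents give no frequency for such cases.
- Pattern 4: the subject is already a Cohort 3 subject with a TEAE, and Table 19 already shows the maximum grade. Recording it as in pattern 6 changes the pooled subject count by 0 and the pooled maximum severity by 0. The number of TEAEs rises by 1, and the new record shows IV as its most recent injection.

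**The case against.** The best defence is that little in the planned tables depends on this, and much of that stands.

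- **Worsening after IV credited to SC.** A reader might infer this from Data Listing 8, and might go on to infer a shift of one subject in six (1/6 = 16.7 points) from IV to SC. The documents do not support either step. No planned AE table separates the routes, SAP 2.2.1 makes by-route analyses optional, and the listing column does not state its reference time. The worsening is unattributable by route; it is not assigned to SC.
- **Bias in the primary endpoint.** A reader might infer this too. Under Protocol 5.3 and 9.2 the endpoint is the proportion of subjects with an ADR, which depends on causality and not on TEAE status. A subject with a related event counts once in Cohort 3 whichever injection was responsible. Tables 16-17 also report all AEs. Left unstated is whether an AE open before injection and made worse by it can count as an ADR.
- **Evidence from the SC pilot.** Protocol 1.2.1 lists fatigue and nausea as possibly related. It gives no duration or course, and the dose was 50 µg with 2.0 mCi. It is no evidence that such symptoms persist or intensify.
- **Few open AEs before injection.** Earlier events are medical history unless procedure-related. Screening consists of examination, ECG, blood and urine collection and photography, and the biopsy follows the IV injection and imaging. This stands.
- **An eCRF guide may cover it.** Protocol 10.1.1 places completion details in a separate document, which might say that worsening opens a new row. Sections 7.5.1 and 7.5.3 also assess AEs before and after the IV injection. This bears on data capture only. It does not change two definitions that look at onset alone, or the requirement for a single maximum grade.

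**Conclusion.** The concern holds in a limited form. Under the stated rules, an AE already open before the first injection stays non-emergent when it worsens, unless the worsening changes management and is entered as a new AE. This applies to procedure-related events under both documents, and to Day 1 pre-injection onsets under the protocol wording only. In Cohort 3, worsening after IV of an AE that began after SC has no date, grade or causality of its own and cannot be attributed to IV.

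The consequence is confined to TEAE Tables 18-19 for the first gap and to route and severity attribution for the second. Pooled Cohort 3 subject counts and maximum severity do not change, and the case for action does not rest on any error in the ADR proportion. The conclusion assumes that sites keep one record per AE, as 8.6.1.3 implies, and that the protocol's TEAE definition refers to the first injection. The change is still worth making: the rule misclassifies some events, the protocol and SAP disagree on the anchor, and grade dates not collected during the study may not be recoverable later.

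**What to change.** 1. **Definition (Protocol 9.5.4 and SAP 5.0).** Use the same wording in both: a TEAE is an AE that starts, or increases in severity category, on or after an injection. Choose one anchor for both documents (date and time, or date only) and say how it applies to the two Cohort 3 injections.
2. **Recording (Protocol 8.6.1.3 and the eCRF instructions).** When severity increases after an injection, including the Cohort 3 IV injection, require a linked AE record with its own onset date and time, grade and causality. The first record keeps the grade reached before that injection.
3. **Counting (SAP 5.0).** Count linked records once per subject in the ADR proportion. State whether an AE open before injection that worsens with a related causality is an ADR.
4. **Display (SAP Tables 16-20, and 21 for consistency).** Show Cohort 3 by most recent injection (SC, IV) as well as pooled, as Tables 22-27 already separate the routes. Without this step the linked records would change only Data Listing 8 and the event counts.

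The cost is one clause in each definition, one eCRF instruction, extra columns in the Cohort 3 shells and an occasional extra AE row. The TEAE event count may be slightly higher, which a footnote on linked records can explain. No extra visit is needed, because AE status is already assessed before and after the IV injection.

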9.5.5 Handling Missing Values

The analysis of the primary efficacy variables will be carried out on the observed data, i.e., a complete case analysis.

9.5.6 Interim Analysis

There are no interim analyses planned for this study.

